## 2.8.4 Supportive analyses

The following supportive analyses will be provided:

- The primary analysis as described in [Section 2.8.2 & Section 2.8.3](#) will be also performed for the PPS, FAS-2 and FAS-3 as supportive efficacy analyses;
- In addition, descriptive summaries will be provided for the FAS-1 by treatment arm:
  - Summary of absolute and relative change from baseline values in serum ferritin assessed at week 25 visit and 95% confidence intervals for means (see [Table 4-2](#) for time window definition);
  - Summary statistics of overall compliance measured by stick pack/tablet count assessed at week 25 visit and 95% confidence intervals for means. Patient who discontinued before the week 25 visit will be included in the compliance endpoint calculation.

These descriptive analyses will be repeated by the age stratification factor, by average actual daily dose category, by baseline serum ferritin category, and underlying disease (see [Table 2-6](#)).

- A forest plot of mean difference between treatments will be presented with absolute change in serum ferritin after 24 weeks of treatment and the corresponding exact 95%CI including these subgroups. Point estimates and 95% CI will be generated.
- If more than 10% of patients have no serum ferritin value after 24 weeks of treatment, sensitivity analysis will be performed for the primary analysis for serum ferritin using multiple imputation method. This analysis will be performed for the FAS-1.

## 2.8.5 Secondary and other analyses of the primary variables

### Secondary analyses of the primary variables

Descriptive summaries as specified in [Section 2.8.4](#) will be repeated:

- For the FAS-1 after 48 weeks of treatment. In addition, if more than 10% of patients have no serum ferritin value after 48 weeks of treatment or missing compliance measured by stick pack/tablet count over 48 weeks of treatment, a sensitivity analysis will be performed using multiple imputation method.
- For the FAS-2 and FAS-3, after 24 and 48 weeks of treatment (as for the FAS-1). Furthermore, a graphical presentation of mean and standard deviation of absolute value in serum ferritin will be plotted by treatment arm and time-window (see [Table 4-2](#) for time-window definition) for FAS-1, FAS-2 and FAS-3.

### Other analyses of the primary variable

Relative and absolute change from baseline in serum ferritin at every year visit during the entire granule period will be described for the Safety Set 4.

## 2.9 Analysis of secondary variables

Secondary variables include patient reported outcomes/observer reported outcomes, safety assessments (i.e. adverse events, laboratory parameters, vital signs, etc.) and

Pharmacokinetics (PKs) parameters. All secondary variables will be analyzed by treatment group.

## **2.9.1 Patient reported outcomes/Observer reported outcomes**

Patient satisfaction, palatability and compliance with study drug will be evaluated for both treatment groups using Patient Reported Outcomes/Observer Reported Outcomes (PRO/ObsRO).

Three PRO/ObsRO questionnaires have been developed: the modified SICT questionnaire, a palatability questionnaire and a compliance diary. Patients/caregiver will complete all PRO/ObsRO questions via a handheld electronic device (exceptionally paper could be used in specific situation). The diaries will be completed daily at home and the palatability and modified SICT will be completed at pre-determined site visits.

The three questionnaires were developed using patient input in one on one interview. The PRO questionnaires were validated for their psychometric properties, and the ObsRO questionnaires will be validated in a within-trial data for validation that will be conducted by Adelphi Value. The statistical analysis plan, the data analysis as well as the results report for ObsRO psychometric validation will be done and provided by Adelphi Value.

[figure not shown]
The FAS-1, FAS-2 and FAS-3 will be used for the three PRO/ObsRO questionnaires analysis for the core phase, unless otherwise specified.

### **2.9.1.1 Modified SICT questionnaire**

#### **Patient reported outcomes**

The Modified SICT questionnaire consists of 13 items that represent 3 domains; Adherence, Preference and Concerns (see [Figure 2-2](#)).

**Figure 2-2** Conceptual model for the Modified Satisfaction with Iron Chelation Therapy questionnaire

**Adherence domain** consists of 7 items, 6 of which are measured using a 5 point response scale.

Items 4 and 5 use the response format 1 “Never”, 2 “Rarely” 3 “Sometimes” 4 “Most of the time” and 5 “Always”; item 6 uses the response format 1 “Always”, 2 “Most of the time” 3 “Sometimes” 4 “Rarely” and 5 “Never”; Item 8 uses the response format 1 “Very easy”, 2 “Easy”, 3 “Neither easy or hard”, 4 “Hard” and 5 “Very hard”; Items 9 and 10 use the response format 5 “Very bothered”, 4 “Bothered” 3 “Moderately bothered”, 2 “A little bothered” and 1 “Not bothered at all”. An Adherence domain score will be calculated by summing these 6 items and as a result a higher score will indicate worse adherence.

Item 7 captures the reasons that the patient did not always take their medication as instructed and is only asked of patients who, at Item 6, indicated that they did not “Always” take their medication as instructed. These patients are instructed to choose all reasons that apply ([Figure 2-3](#)). Each response category will be coded as binary item, for example taste will be an item with the response format 0 “Not endorsed” 1 “Endorsed”.

**Figure 2-3      Conceptual model for Item 7 of the modified SICT**

**Satisfaction/preference domain** consists of 3 items, 2 (Items 11 and 12) assess the patients' satisfaction with the medication and are measured using a 5 point response scale with the response format 1 "Very satisfied", 2 "Satisfied", 3 "Neither satisfied nor dissatisfied", 4 "Dissatisfied" 5 "Very dissatisfied". A Satisfaction domain score will be calculated by summing these two items. Higher scores will indicate worse satisfaction.

[figure not shown]
The third item (Item 13) asks the patient to assess which medication for iron overload they prefer.

**Concerns domain** consists of 3 items (Items 1, 2 and 3) to address any concerns and worries the patient has with their medication. All 3 items are measured on a 5 point response scale with the response format 1 "Always", 2 "Most of the time", 3 "Sometimes", 4 "Rarely" and 5 "Never". A Concerns domain score will be calculated by summing these 3 items. Higher scores will indicate fewer concerns.

### **Observer reported outcomes**

The modified SICT consists of 17 items that represent 3 domains: Adherence, Preference, and Concerns (see [Figure 2-4](#)).

**Figure 2-4** Conceptual Model for the Modified Satisfaction with Iron Chelation Therapy Questionnaire

The conceptual framework consists of 2 separate scales to capture the child's and caregiver's perspective; these are further broken into 3 domains for the child: Concerns, Preference, and Adherence and 2 domains for the caregiver: Concerns and Adherence.

**Adherence** domain will be captured from 2 perspectives:

- Child's perspective (a Domain score + a Checklist for reasons for non-adherence)
- Caregiver's perspective (a Domain score + a Checklist for reasons for non-adherence)

There will be 2 separate domain scores for overall adherence, the caregiver's perspective of adherence domain consists of 6 items (Items 12, 13, 14, 16 and 17), while the child's perspective of adherence domain consists of 7 items (Items 3, 4, 5, 7, 8 and 9).

**Child's perspective of Adherence:** Items 3 and 5 are measured using a 5-point response scale: "Always" =1, "Most of the time" =2, "Sometimes" =3, "Rarely" =4, and "Never" =5. Item 4 is measured on a scale from "Always" =5, "Most of the time" =4, "Sometimes" =3, "Rarely" =2, and "Never" =1. Two items (Item 7 and 8) use different response options. Item 7 focuses on "How easy/hard did your child tell you it was to take his/her medicine" and uses the response scale "Very easy" =1, "Easy" =2, "Neither easy or hard" =3, "Hard" =4, and "Very hard" =5. Similarly, Item 8 captures bother expressed by child for amount of time he/she had to wait to eat food after taking medication. The response scale for Item 8 is "Very bothered" =5, "Bothered" =4, "Moderately bothered" =3, "A little bothered" =2, and "Not bothered at all" =1. Item 9 reports "how happy your child appeared" and is scored on a scale from 1=Very happy and 5=Very unhappy.

[figure not shown]
**Caregiver's perspective of Adherence:** Items 12 and 14 are measured using a 5-point response scale: "Always" =1, "Most of the time" =2, "Sometimes" =3, "Rarely" =4, and "Never" =5. Conversely, Item 13 is scored as "Always" =5, "Most of the time" =4, "Sometimes" =3, "Rarely" =2, and "Never" =1. Two items (Item 16 and 17) use different response options. Item 16 focuses on "How easy/hard was it to give your child his/her medicine" and uses the

response scale “Very easy” =1, “Easy” =2, “Neither easy or hard” =3, “Hard” =4, and “Very hard” =5. Similarly, Item 17 captures “bothered by the amount of time it took to prepare medication” and uses the response scale “Very bothered” =5, “Bothered” =4, “Moderately bothered” =3, “A little bothered” =2, and “Not bothered at all” =1.

Separate adherence domain score for the child’s and caregiver’s perspective will be calculated. A domain score will be calculated by summing item scores on respective domains. Overall, a lower domain score will indicate better adherence.

The checklist item from each perspective will evaluate the reason for non-adherence. Only respondents who, at Item 5 (for the child’s perspective) and Item 14 (for the caregiver’s perspective), indicate that they did not “Always” take their medication as instructed, are expected to give the reasons for non-adherence. For both perspectives the respondent can check all the reasons that apply (Figure 2-5). For the child’s perspective (item 6), each of the 5 response options (i.e. taste, aftertaste, inconvenience, prepared medicine incorrectly, and other) will be coded as binary item, for example taste will be an item with the response format 0 “Not endorsed” 1 “Endorsed”. Similarly, for the caregiver perspective (item 15), each of the 7 response options (i.e. child refuse to take, forgot, inconvenient, side-effect, not prepare medication per doctor’s instruction, did not give full amount, and others) will be coded as binary item (0/1).

**Figure 2-5**      **Conceptual model for item 6 and item 15 of the modified SICT**

**Preference of the Child:** This domain consists of 1 item (Item 10), to assess which medication they prefer (like). The item is to be considered a single item domain.

**Concerns domain** will be captured from 2 perspectives:

- Child’s perspective (Item 1 and 2)
- Caregiver’s perspective (Item 11)

The concerns domain for the child’s perspective has 2 items which focus on “limiting child’s activity” (Item 1) and “getting upset about the side-effects” (Item 2). Both the items are

measured using a 5-point response scale from “Always” =1, “Most of the time” =2, “Sometimes” =3, “Rarely” =4, and “Never” =5. A sum score for a Concerns domain for the child's perspective will be created. A higher score will indicate lesser concerns.

There is only a single item to capture concern in regards to caregiver's perspective. The item 11 captures “worry if the child is swallowing enough medication” and is scored on a 5-point response scale from “Always” =1, “Most of the time” =2, “Sometimes” =3, “Rarely” =4, and “Never” =5. A higher score on the single item domain will indicate lesser caregiver concern.

Adherence, satisfaction/preference and concerns domain scores will be summarized using standard descriptive statistics by treatment arm, type of questionnaire (ObsRO questionnaire versus PRO questionnaire) and week (weeks 2, 3, 25 and core EOT). Additionally, absolute change from week 2 to week 25 and core EOT in the domain scores will be summarized including 95% confidence intervals for mean.

Graphical representation of PRO scores over weeks will be provided by domain by type of questionnaire and treatment. The y-axis will be the mean and SD for the domain score and the x-axis will be the week number.

In addition, all items from adherence, satisfaction/preference and concerns domains will be summarized by treatment arm by type of questionnaire and week using frequency counts and percentages for the FAS-3.

The number of patients completing the modified SICT questionnaire and the number of missing or incomplete assessments will be summarized by treatment arm, type of questionnaire and week for the FAS-3.

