### 7.2.3 Patient / Observer Reported Outcomes

Patient satisfaction, palatability and compliance will be measured for both formulations using Patient / Observer Reported Outcomes (PRO/ObsRO) questionnaires.

For patients aged between 10 years and less than 18 years at enrollment, the PRO questionnaires will be completed by the patients themselves. The questionnaires for patients aged between 2 years and less than 10 years have been designed as observations made by caregivers such as the parent or legal guardian (ObsRO). For these patients the caregivers will continue completing the ObsRO questionnaires even after the patient turns 10 years for consistency in responses.

Three questionnaires were developed to evaluate both formulations: the modified Satisfaction with Iron Chelation Therapy (SICT), a palatability questionnaire and a compliance diary. All questions will be translated into the patient's native language.

All Patients/caregivers will complete the PRO/ObsRO questions via a handheld electronic device and they will receive training on the operation of this device. The device will be programmed to ensure that all relevant observations are recorded before submission.

In case of malfunctioning devices (confirmed by vendor support helpdesk and only under this condition, the patients/caregivers will be authorized to use paper questionnaires until vendor fixes issue(s) of devices. The back-up paper entry process in case of technical issues must be followed before any reporting in the database.

The modified SICT questionnaire will be completed at Visits 4 (Week 2), 5 (Week 3), 11 (Week 25), and 777 (within 7 days of the last dose of treatment for those not continuing to the extension phase). The Visit 4 assessment will be considered as baseline since the questionnaire asks for patient's satisfaction with the iron chelation therapy received 'in the past week'. The rationale for having the modified SICT completed also at Visit 5 is based on the need to conduct a test-retest reliability within trial, meaning that patients need to complete the modified SICT questionnaire within 2-14 days after the baseline data collection to ensure the stability of the measure over a period of time where little change would be expected.

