### **10.5.3 To evaluate both formulations on patient satisfaction and palatability using PRO/ObsRO questionnaires**

The FAS-1, FAS-2 and the FAS-3 will separately be used for the analysis of patient satisfaction and palatability using a PRO/ObsRO questionnaire for the core phase.

For the SICT questionnaire, the score for each domain will be the mean of the score of items included in the corresponding domain. Standard descriptive analyses will be performed for both formulations for each domain score at Week 2, Week 3, Week 25 and the EOT (core)/777 visits as well as their absolute changes at Week 25 and EOT (core)/777 visits from Week 2. The standard descriptive analyses include: n, mean, standard deviation, minimum, median and maximum. The 95% confidence intervals for the absolute changes in all domains at Week 25 and EOT (core)/777 visits from Week 2 will be presented for both formulations.

For the palatability questionnaire the overall score will be constructed using a scoring matrix from the score of items. Standard descriptive analyses will be performed for both formulations for the overall score at the Week 2, Week 3, Week 25 visits, and last day of study drug intake and the absolute changes of the overall score at the Week 25 visit and last day of study drug from Week 2. The standard descriptive analyses include: n, mean, standard deviation, minimum, median and maximum. The 95% confidence interval for the absolute change of the overall score at the Week 25 visit and last day of study drug from Week 2 will be presented for both formulations.

Details about scoring and analyses will be included in the SAP.

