**Table 2-3      Scoring Matrix**

Palatability Score	Item1 – taste	Item3 – what happened	Item4 – amount	Definition
0	Bad & Very bad; 2	Vomited < 30 min; 3	Not enough too much; 1	Worst palatability
1	Bad & Very bad; 2	Vomited < 30 min; 3	Just enough; 2	1
2	Bad & Very bad; 2	Spat some/ all out; 2	Not enough too much; 1	2
3	Bad & Very bad; 2	Spat some/ all out; 2	Just enough; 2	3
4	Bad & Very bad; 2	Swallowed all; 1	Just enough; 2	4
5	Bad & Very bad; 2	Swallowed all; 1	Not enough too much; 1	5
6	V. good, Good & Not good/bad; 1	Vomited < 30 min; 3	Not enough too much; 1	6
7	V. good, Good & Not good/bad; 1	Vomited < 30 min; 3	Just enough; 2	7
8	V. good, Good & Not good/bad; 1	Spat some/ all out; 2	Not enough too much; 1	8
9	V. good, Good & Not good/bad; 1	Spat some/ all out; 2	Just enough; 2	9
10	V. good, Good & Not good/bad; 1	Swallowed all; 1	Not enough too much; 1	10
11	V. good, Good & Not good/bad; 1	Swallowed all; 1	Just enough; 2	Best palatability

The palatability summary score will be summarized using descriptive statistics by treatment arm, type of questionnaire (ObsRO questionnaire versus PRO questionnaire) and week (weeks 2, 3, 25 and core EOT). Additionally, absolute change from week 2 to week 25 and core EOT will be summarized including 95% confidence intervals for mean.

Graphical representation of this 11 point response scale will be provided over weeks by treatment and type of questionnaire. The y-axis will be the mean and SD and the x-axis will be the week number.

In addition, all of the 4 Items from the palatability questionnaire will be summarized using descriptive statistics by treatment arm, type of questionnaire and week using frequency counts and percentages for the FAS-3.

The number of patient completing the palatability questionnaire and the number of missing assessments will be summarized by treatment arm, type of questionnaire and week for the FAS-3.

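### Satisfaction and palatability scores get a 95% CI only for within-arm change from week 2, an on-treatment value, and no granule-minus-DT contrast is planned.

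*SAP*

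**What the plan says.** The objective in Protocol Table 3-1 is to evaluate both formulations on satisfaction and palatability.

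- **Levels by visit.** For the SICT, the primary-analysis SAP (Amendment 3, 2.9.1.1) says that the "domain scores will be summarized using standard descriptive statistics by treatment arm, type of questionnaire (ObsRO questionnaire versus PRO questionnaire) and week", at weeks 2, 3, 25 and core EOT. For palatability (2.9.1.2), "The palatability summary score will be summarized using descriptive statistics by treatment arm, type of questionnaire" and by the same weeks. Protocol 10.5.3 defines the content: "The standard descriptive analyses include: n, mean, standard deviation, minimum, median and maximum". No interval is included.
- **Plots.** For the SICT, "The y-axis will be the mean and SD for the domain score and the x-axis will be the week number". The palatability plot is also mean and SD by week and treatment. Individual items are tabulated as counts and percentages in FAS-3.
- **Intervals.** For the SICT, "absolute change from week 2 to week 25 and core EOT in the domain scores will be summarized including 95% confidence intervals for mean". For palatability, "absolute change from week 2 to week 25 and core EOT will be summarized including 95% confidence intervals for mean". Protocol 10.5.3 agrees: "The 95% confidence intervals for the absolute changes in all domains at Week 25 and EOT (core)/777 visits from Week 2 will be presented". These intervals are within each arm. The End-of-Core SAP (2.9.5.1 and 2.9.5.2) repeats this plan.
- **Status of week 2.** Protocol 7.2.3 says: "The Visit 4 assessment will be considered as baseline since the questionnaire asks for" satisfaction over the preceding week. It also calls the Visit 4 palatability score a baseline. The Amendment 4 rationale (item 14) says that the week 2 assessment is not to be treated as a baseline, and the analysis text refers only to week 2.

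**The concern.** The first questionnaire is completed at Visit 4 (week 2). The SICT asks about the past week, and by then the child has been taking the randomised formulation for about that week. The week 2 score is thus an outcome under the assigned treatment, and subtracting it removes whatever formulation effect is already there.

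This matters because of how the granules are meant to help. Protocol 2.1 bases the case for them on taste, convenience, freedom to take the dose with food, and changed excipients. Taste and convenience at least could act from the first doses. If they do, the interval sits on a quantity that says little about which formulation children and caregivers find better. The tables that do bear on that question carry no measure of precision for the comparison.

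**Working it through.** The documents give no SD, effect size or sample size for these scores, so there is no figure of theirs to reproduce. The check is on what the planned quantity estimates.

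**Inputs from the documents**
- Week 2 is planned for study day 8, where day 1 is the first treatment day (SAP Table 4-2, which sets visit timing for laboratory data and vital signs).
- SICT recall is the past week (Protocol 7.2.3). No recall period is stated for palatability.
- There are 48 ICT-naïve patients per arm and up to 108 per arm overall (SAP 2.11).

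**Assumptions**
- Scores are in SD units (SD 1 at each visit).
- Within-patient correlation between visits is 0.3 to 0.7.
- 24 per arm stands for a smaller subset, such as one questionnaire type.

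**Step 1: what the change estimates.** Let the DT mean at week t be m(t) and the granule mean be m(t) + d(t), where d(t) is the formulation effect.
- DT change from week 2 to 25: m(25) − m(2).
- Granule change: m(25) − m(2) + d(25) − d(2).
- Between-arm difference in change: d(25) − d(2).

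| Effect at week 2 | Effect at week 25 | Difference in change |
|---|---|---|
| 0.50 | 0.50 | 0.00 |
| 0.80 | 0.80 | 0.00 |
| 0.50 | 0.70 | 0.20 |
| 0.25 | 0.50 | 0.25 |
| 0.00 | 0.50 | 0.50 |

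A constant effect cancels whatever its size. A growing effect cancels in part. A fading one leaves a remainder of the opposite sign: 0.50 falling to 0.25 gives 0.25 − 0.50 = −0.25, although granules are still ahead. Only an effect absent at week 2 is kept whole. On the 0–11 palatability score, a steady gap of 3 points (illustrative) with no drift over time gives a change of 0 in each arm.

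**Step 2: precision of the missing contrast.** The half-width of a 95% CI for the between-arm difference in level is t(0.975, 2n−2) × √(2/n):
- n = 24 per arm: 0.58 SD
- n = 48 per arm: 0.41 SD
- n = 108 per arm: 0.27 SD

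For the between-arm difference in change, multiply by √(2(1−ρ)), where ρ is the within-patient correlation. At 48 per arm this gives 0.48, 0.41 and 0.31 SD for ρ = 0.3, 0.5 and 0.7.

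**Step 3: illustration.** In 20,000 simulated trials with 48 per arm, ρ = 0.5 and a constant effect of 0.5 SD:
- Difference in level at week 25: mean 0.50 SD, CI excludes zero in 68%.
- Difference in change from week 2: mean 0.00 SD, CI excludes zero in 5%, the rate expected with no effect.

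The plan gives not even this second contrast. It gives one interval per arm, for the reader to compare.

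**The case against.** The strongest reply is that nothing is lost from the report. Scores by arm and week come first in the plan, and change from week 2 is an addition. With n, mean and SD in each arm, a reader can see a steady difference and can compute an unadjusted interval. This stands. A reader might infer that the planned analysis cannot reveal a formulation effect, or that the effect disappears from the results. The documents do not support that: by-arm levels, plots by treatment and item frequencies are all planned.

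Second, no formal inference is planned for these scores, and hypothesis tests are confined to the co-primary endpoints. This also stands, so the point is not that a test is misdirected. But being descriptive does not explain where the interval was put: SAP 2.8.4 gives between-treatment differences in serum ferritin with 95% CIs in a descriptive forest plot.

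Third, full cancellation needs the same effect at week 2 and later. It is tempting to assume this for every domain, but the documents give no time course. It is plausible for taste and less so for concerns about side effects or for adherence, which may shift over months.

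Fourth, the trial is open-label, so self-reported differences may partly reflect expectation, which an interval does not correct. Also, the final SAP (Table 1-1) states that these results were presented in the End-of-Core report and will not be repeated. Both points limit what the addition can claim. Neither supports keeping the interval on the change alone.

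**Conclusion.** The concern holds in a limited form. For the SICT domain scores and the palatability score, the only interval is on the within-arm change from an on-treatment value, and no interval or contrast compares the formulations. An effect present at week 2 cancels from that quantity, fully if constant and in part if it grows or fades. The algebra needs no distributional assumption. The 68% against 5% rests on the assumed SD, correlation, effect and 48 per arm, and is only an illustration.

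The consequence is moderate. The comparison can be read from the by-visit tables, but without stated precision or adjustment. The primary analysis and the sample size are not affected. A reader might also take the word baseline in Protocol 7.2.3 to mean that a pre-treatment reference is assumed in the analysis. The analysis text does not do that, so aligning the wording is editorial.

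**What to change.** In SAP 2.9.1.1 and 2.9.1.2, and in End-of-Core SAP 2.9.5.1 and 2.9.5.2, add the granule-minus-DT difference in mean score with a 95% CI at weeks 2, 3, 25 and core EOT.

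- **Scores:** the summed SICT domain scores, the single caregiver concern item (ObsRO item 11) and the palatability score. Leave the single-item preference questions (PRO item 13, ObsRO item 10) as frequencies.
- **Strata:** report by questionnaire type (PRO or ObsRO), which follows the age stratum. In FAS-3, adjust for prior ICT.
- **Labels:** descriptive, not adjusted for multiplicity, subject to open-label reporting bias, and post hoc if added after the End-of-Core report.
- **Change from week 2:** keep it, described as durability on treatment.
- **Protocol 7.2.3:** align the baseline wording with the Amendment 4 rationale.

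The data are already collected, so the cost is SAP and table-shell wording and a little programming. The tables get longer: 4 PRO scores (adherence, satisfaction, concerns, palatability) and 5 ObsRO scores (child adherence, caregiver adherence, child concerns, caregiver concern, palatability) at 4 visits make (4 + 5) × 4 = 36 intervals per analysis set. This is why the descriptive label is needed.
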